6.2 Handling of Dropouts or Missing Data

No data imputation will be performed for missing efficacy and safety variables, except efficacy endpoints of percentage of subjects castrated. If E₂ measurement is missing, the last available E₂ measurement at post-baseline visits will be used in deriving subjects castrated.

For laboratory values or concentration data below the lower limit of quantification (LLOQ) like “<xxx” or “<=xxx”, or above the upper limit of quantification (ULOQ) like “>xxx” or “>=xxx”, LLOQ or ULOQ

Statistical Analysis Plan

Version: Final 3.1

Date of Issue: 13DEC2019

Ipsen Pharma; Protocol No. D-CN-52014-220

CCI

(xxx) will be used for calculation of descriptive statistics. The original laboratory values or concentration data (“<xxx”, “<=xxx”, “>xxx” or “>=xxx”) are presented in the listing.

6.2.1 Handling of triptorelin BLQ concentration values

For the full PK/PD subgroup (with full PK sampling schedule) only, and for descriptive statistics only (not for the individual listings):

- For the first administration of study drug, BLQ data must be substituted by 0 for concentrations measured before the first quantifiable concentration, and by missing after the first quantifiable concentration.
- For any other administration all BLQ must be set as missing in the dataset

For the sparse PK groups all BLQ must be set as missing in the descriptive statistics datasets.

For further details of the descriptive statistics for triptorelin concentration data please refer to [section 7.8](#).

6.2.2 Partial dates

If the date of endometriosis diagnosis or date of endometriosis surgery is a partial date, the first day of known year and/or month will be used to calculate duration.

For AEs, concomitant medications, and concurrent procedures, the following conventions will be used for imputing partial dates:

- If day (and month) is missing for AE onset date, or start date of a concomitant medication, or date of concurrent procedure, the partial date will be set to
 - date of first dose of IMP, if the known year (and month) is same as the year (and month) of first dose of IMP and no other information indicating the date is before first dose of IMP;
 - the first day of the known year (and month), if the year (and month) of the partial date is different from the year (and month) of the first dose of IMP or other information indicating the date is before first dose of IMP;
- If day (and month) is missing for AE stop date, or the stop date of a concomitant medication, this day will be set to the last day of the known year (and month) that AE or medication occurred;
- If AE onset date, or start date of a concomitant medication, or date of concurrent procedure is completely missing, this date will be set to date of the dose of IMP;
- If the imputed start date is after stop date, the start date will be set to the stop date.

Partial dates will be presented as original in all listings, and imputed dates will not be presented in listings.

6.3 Pooled Center

If cities have number of PP subjects less than average number of subjects per centre (total number of PP subjects divided by total number of centres), these cities will be pooled together or pooled to other cities to keep all cities with number of subjects equal to or more than average number of subjects per centre.

7 STATISTICAL METHODS

7.1 General Principles

The statistical analyses will be performed in accordance with ICH E9 guideline ^{1,3,4}.

Statistical analysis of the efficacy and safety data will be performed by Covance, managed by the Sponsor's Biometry Department.

All data processing, summarisation and analyses will be performed using Version 9.3 (or higher) of the Statistical Analysis System (SAS[®]) statistical software package.

Unless specified otherwise, data will be displayed using the following treatment group labels, in the order presented:

Triptorelin Pamoate PR 3-month

Triptorelin Acetate PR 1-month

Total (if total is presented for all treatment groups)

Continuous variables will be summarised by the number of subjects (n), mean, standard deviation (SD), median, minimum and maximum. The summary statistics will be displayed for visits where there are non-missing data for at least two subjects in one or more treatment groups. Mean, median and SD will have 1 extra decimal place than the actual values. If 95% CI of mean is presented, lower and upper confidence interval values should be presented to one decimal place more than the raw/derived data (i.e. to the same number of decimal places as the mean). Minimum and maximum values will be reported with the same decimal places as the actual values. A maximum 3 decimal places will be displayed for all summary statistics.

For categorical variables, summaries will include counts of subjects or events and percentages (1 decimal), 0% will not be presented. Percentages will be calculated using a denominator of all subjects in a specified population unless otherwise specified. The denominator will be specified in a footnote to the tables for clarification if necessary. Percentages in the summary tables will be rounded and thus may not always add up to exactly 100 percent. The 95% CI of rate or rate difference will have 2 decimal places.

In the summary tables, p-values will be rounded to 4 decimal places if appropriate. If a p-value is greater than 0.9999, then ">0.9999" will be presented; if a p-value is less than 0.0001, then "<0.0001" will be presented.

All data collected during the study will be presented in listings by treatment group, study centre, subject identifier, and visit (where applicable), unless otherwise specified.

All text fields must be left justified and numeric or numeric with some text specification (e.g.: not done, unknown, <4.5 ...) must be decimal justified. Dates will be presented in the format [ddMMMyyyy] and times in the format [hh:mm] in a 24-hour basis.

7.2 Subject Disposition and Data Sets Analysed

Subject disposition will be listed and summarised by treatment group and overall and the following subjects will be presented:

- Number of subjects screened (overall);
- Number of screen failures and reason for non-randomised subjects (overall)

Statistical Analysis Plan

Version: Final 3.1

Ipsen Pharma; Protocol No. D-CN-52014-220

Date of Issue: 13DEC2019

CCI

- Number of subjects randomised;
- Number of subjects randomised and not treated;
- Number of subjects treated;
- Number of subjects who completed Week 12, Week 24 and study;
- Number of subjects discontinued study, and reason for discontinuation;
- Number of subjects included in each analysis set (Randomised, Safety, FAS, PP, Full PK Profile, Sparse PK Sampling, PD, PK/PD Relationships).

A summary of subject enrollment by centre will also be provided by treatment group and overall for the randomised subjects.

A summary of subjects completed scheduled visits will be presented by treatment group and overall for the randomised subjects.

7.3 Protocol Deviations

Major protocol deviations affecting primary efficacy endpoint leading to exclusion from the PP set will be summarised by treatment group and overall for the randomised subjects.

Major protocol deviations affecting PK variables leading to exclusion from the Full PK Profile Analysis Set and/or Sparse PK Sampling Analysis Set will also be summarised by treatment group and overall for the safety set.

All protocol deviations will be listed for the randomised subject with flags indicating if deviations are major or minor PDs.

A separate listing for major protocol deviations will be displayed. Flags indicating deviations affecting efficacy endpoints and/or PK/PD variables will also be included in the listing.

7.4 Demographics and Other Baseline Characteristics

Demographic and baseline characteristics will be listed and summarised by treatment group and overall for these analysis sets: randomised, safety (if different from randomised), PP and FAS, including the below variables:

- Age (years) is reported from CRF;
- Race, Ethnicity;
- Weight (kg), height (cm), body mass index (kg/m^2) (BMI) [calculated as $(\text{weight}/\text{height}^2)$ where weight is in kg and height is in m];
- Gynaecological history:
 - Duration of endometriosis diagnosis (months) [calculated as $(\text{informed consent date} - \text{date of endometriosis diagnosis} + 1) / 30.4375$ and rounded to 1 decimal place];
 - Method of diagnosis
 - If having endometriosis surgery before; duration of endometriosis surgery (months) [calculated as $(\text{informed consent date} - \text{date of endometriosis surgery} + 1) / 30.4375$ and rounded to 1 decimal place];

Statistical Analysis Plan

Version: Final 3.1

Date of Issue: 13DEC2019

Ipsen Pharma; Protocol No. D-CN-52014-220

CCI

- Age at menarche, number of pregnancies, number of births
- If having regular menses during the last six months
- Number of days for shortest cycle and Number of days for longest cycle

Standard descriptive statistics will be presented for the continuous variables and the total counts and percentages of subjects will be presented for the categorical variables. No formal tests of statistical significance will be performed on the demographic and baseline data.

Other baseline measurements (such as E₂, FSH and LH concentrations, VAS, lab test, vital signs, ECG, physical/pelvic examination, pelvic type B ultrasound scan) will be summarised by treatment group with the post-baseline measurements.

7.4.1 Medical History

Medical history will be coded using the Medical Dictionary for Regulatory Activities (MedDRA) (version number is the newest version used in Covance coding system at the time of analysis). All medical history will be listed and summarised by the number and percentage of subjects with any medical history for randomised set by system organ class (SOC) and preferred term (PT) for each treatment group and overall.

7.4.2 Previous and Concomitant Medications

Prior medications for endometriosis and other medications received prior to or concomitantly with study treatment will be coded using the WHO Drug Dictionary (version number is the newest version used in Covance coding system at the time of analysis), Anatomical Therapeutic Chemical (ATC) Classification codes.

Prior medications for endometriosis from eCRF will be summarised separately by the number and percentage of subjects with any medications for randomised set by anatomical level (ATC Level 1), therapeutic level (ATC Level 2) and generic term for each treatment group and overall.

Prior medications are those taken prior to first study dose of IMP. Concomitant medications are those taken on or after the first dose of IMP.

Prior medications and concomitant medications will be summarised separately by the number and percentage of subjects with any medications for randomised set by anatomical level (ATC Level 1), therapeutic level (ATC Level 2) and generic term for each treatment group and overall.

The number and percentage of subjects taking add-back treatment during the study will be summarised separately by anatomical level (ATC Level 1), therapeutic level (ATC Level 2) and generic term for each treatment group and overall.

Prior medications for endometriosis will be separately listed. Prior and concomitant medications will be presented in the same listing with flags indicating prior or concomitant.

7.4.3 Previous and Concomitant Non-drug Therapies

Prior and concomitant non-drug therapies will be coded using MedDRA (version number is the newest version used in Covance coding system at the time of analysis). All prior and concomitant non-drug therapies will be listed and summarised by the number and percentage of subjects with any non-drug therapies for randomised set by system organ class (SOC) and preferred term (PT) for each treatment group and overall.

Statistical Analysis Plan

Version: Final 3.1

Ipsen Pharma; Protocol No. D-CN-52014-220

Date of Issue: 13DEC2019

CCI

Prior non-drug therapies are those taken prior to first study dose of IMP. Concomitant non-drug therapies are those taken on or after the first dose of IMP.

Prior non-drug therapies and concomitant non-drug therapies will be summarised separately by the number and percentage of subjects with any therapies for randomised set by therapy reason for each treatment group and overall.

Prior and concomitant non-drug therapies will be presented in the same listing with flags indicating prior or non-drug therapies.

7.4.4 Concomitant Surgical Procedures

Concomitant surgical procedures will be coded using the MedDRA (version number is the newest version used in Covance coding system at the time of analysis). All concomitant surgical procedures will be listed and summarised on the number and percentage of subjects with any surgical procedures for randomised set by surgical reason, SOC and PT for each treatment group and overall.

Concomitant surgical procedures will be presented in the listing.

7.5 Study Drug Administration

Study drug administration will be summarised separately through Week 12 and Week 24 by treatment group and overall for safety subjects, including the below variables:

- Number of injections during Week 12, Week 24
- Total actual dose during Week 12, Week 24
- Treatment compliance through Week 12, Week 24 and compliance groups (grouped as <80%, 80-120%, >120%)

Standard descriptive statistics will be presented for the continuous variables and the total counts and percentages of subjects will be presented for the categorical variables. No formal tests of statistical significance will be performed on the study drug administration.

Treatment compliance will be calculated as follows:

- Treatment compliance through Week 12 in triptorelin pamoate PR 3-month group = $100\% * \text{actual dose administered before Week 12} / (\text{total planned dose administered before Week 12})$;
- Treatment compliance through Week 24 in triptorelin pamoate PR 3-month group = $100\% * \text{sum of actual dose administered through Week 24} / (\text{total planned dose administered through Week 24})$;
- Treatment compliance through Week 12 in triptorelin acetate PR 1-month group = $100\% * \text{sum of actual dose administered before Week 12} / (\text{total planned dose administered before Week 12})$.
- Treatment compliance through Week 24 in triptorelin acetate PR 1-month group = $100\% * \text{sum of actual dose administered through Week 24} / (\text{total planned dose administered through Week 24})$.

7.6 Efficacy

7.6.1 Primary Efficacy Analysis

The primary efficacy analysis is to compare the percentage of subjects castrated ($E_2 \leq 184$ pmol/L or 50 pg/mL) at Week 12 in triptorelin pamoate PR 3-month and triptorelin acetate PR 1-month groups on the PP subjects using as-treated assignments.

The null hypothesis for the primary efficacy analysis is that triptorelin pamoate PR 3-month is inferior to triptorelin acetate PR 1-month. The alternative hypothesis is that triptorelin pamoate PR 3-month is noninferior to triptorelin acetate PR 1-month, where the pre-specified non-inferiority margin is -10%:

$$H_0: P_{3\text{-month}} - P_{1\text{-month}} \leq -10\%$$

$$H_a: P_{3\text{-month}} - P_{1\text{-month}} > -10\%$$

Where $P_{3\text{-month}}$ denotes the percentage of subjects ($E_2 \leq 184$ pmol/L or 50 pg/mL) for triptorelin pamoate PR 3-month at Week 12, $P_{1\text{-month}}$ denotes the percentage of subjects ($E_2 \leq 184$ pmol/L or 50 pg/mL) for triptorelin acetate PR 1-month at Week 12.

The number and percentage of subjects castrated ($E_2 \leq 184$ pmol/L or 50 pg/mL), and its 95% asymptotic CI will be summarised for each treatment group at Week 12. The difference in percentage of subjects castrated (triptorelin pamoate PR 3-month – triptorelin acetate PR 1-month) and the 2-sided 95% CI of the difference will also be presented and calculated using the Miettinen and Nurminen method, stratified by randomisation stratification factors (endometriotic surgical history and the severity of endometriosis-associated pelvic pain at baseline) with sample size weighting⁵. In a case where the stratification factor recorded in the eCRF and IWRS are inconsistent, the eCRF data will be retained included as the randomization stratification factors as the covariates. If the lower limit of the 95% CI for the difference is $> -10\%$, triptorelin pamoate PR 3-month non-inferiority to triptorelin acetate PR 1-month will be confirmed.

The sensitivity analysis will be performed on the same analyses adding centre in the above Miettinen and Nurminen method.

The difference in percentage and its 2-sided 95% CI are also calculated using the Miettinen and Nurminen method without stratification factors for support analyses.

The primary efficacy analyses will be repeated for the FAS subjects using as-randomised assignments.

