1.3 Findings from Clinical Studies

The efficacy of triptorelin in the treatment of endometriosis is well established [4]. Clinical studies have demonstrated rapid and sustained biochemical castration and improvement in the signs and symptoms of endometriosis. Consequently, various triptorelin formulations are approved for the treatment of endometriosis in different territories, including triptorelin acetate PR 1-month in China.

The pharmacodynamic (PD) and pharmacokinetic (PK) equivalence of triptorelin pamoate PR 3-month to triptorelin acetate PR 1-month with endometriosis was previously investigated in female European subjects in Ipsen Study E-28-52014-705 [5]. In this study, a total of 146 subjects received either a single dose of triptorelin pamoate PR 3-month (72 subjects) or triptorelin acetate PR 1-month (74 subjects) over 3 months. At 12 weeks, the efficacy of triptorelin pamoate PR 3-month (as determined by the percentage of subjects with E₂ concentrations suppressed to castration levels) was found to be noninferior to the 1-month formulation. Overall, 97% of subjects receiving triptorelin pamoate PR 3-month were castrated at Week 12, compared to 94% receiving the 1-month formulation.

Further details may be found in the IB.

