3 STUDY DESIGN

3.1 General Design and Study Schema

This is a prospective, phase III, multicentre, randomised, open-label, parallel group, active-controlled study. A total of 300 Chinese female subjects with endometriosis will be randomly assigned in a 1:1 ratio to triptorelin pamoate PR 3-month or triptorelin acetate PR 1-month. Specific details of the dosage groups are given in Section 6.

Subjects will be recruited and screened for eligibility up to 5 weeks prior to the first dose of investigational medicinal product (IMP) being administered. The first dose of IMP must be initiated at the baseline Visit (Day 1) in the follicular phase of subjects (the first to fifth day of the menses period). The treatment period will be 24 weeks, with the schedule of injections being once per 12 weeks for triptorelin pamoate PR 3-month (with subjects in this group receiving a total of two injections, one each at baseline and Week 12), or once per 4 weeks for triptorelin acetate PR 1-month (with subjects in this group receiving a total of six injections, one each at baseline and Weeks 4, 8, 12, 16 and 20). The subjects visit the study site every 4 weeks until Week 24, with the exception of the subgroup participating in the full PK and exploratory PD evaluations (up to 32 subjects, including up to 16 from each treatment group; to be enrolled at selected sites), who will have additional study visits. "Add back" treatment (recommended as, but not limited to, tibolone 2.5 mg once daily) may be administered after 12 weeks if needed based on the investigator's judgement. After 24 weeks' treatment, the subject will be followed up once every 4 weeks via telephone (except for subjects receiving triptorelin pamoate PR 3-month and participating in the full PK/PD subgroup, who will visit the study site) until menses recovery or Week 40 (whichever is earlier). The first visit after the menses recovery or Week 40 will be considered as the end of study visit. All subjects will attend the study site for the end of study visit. The principal study design features are summarised in Figure 1.

Figure 1 Study Design

[a] additional visits for subjects in the PK/PD subgroups not indicated

[b] during follow up, the first visit after menses recovery, or Week 40 (whichever is earlier) is considered the end of study visit

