2.3 Sample Size and Power

The sample size was estimated based on data from Ipsen Study E-28-52014-705. Assuming the percentage of subjects castrated at Week 12 of triptorelin acetate PR 1-month treatment is no less than 92%, a sample size of 133 subjects in each treatment group will have 85% power to demonstrate the noninferiority of

Statistical Analysis Plan

Version: Final 3.1

Ipsen Pharma; Protocol No. D-CN-52014-220

Date of Issue: 13DEC2019

CCI

triptorelin pamoate PR 3-month to the comparator, when the lower limit of the 95% confidence interval (CI) of the difference in percentage of subjects castrated at Week 12 between the treatment groups is $\geq -10\%$ and with a 0.025 one-sided type I error rate.

Assuming that the dropout rate will be around 10%, a sample size of 300 randomised subjects in total is planned for this study.

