7.6.3 Subgroup Analysis

The primary efficacy endpoints and secondary efficacy endpoints (except time to menses recovery) will be analysed by subgroups of randomisation stratification factors:

- Endometriotic surgical history (previous surgery, no previous surgery)
- Severity of endometriosis-associated pelvic pain at baseline (VAS>3 cm, VAS≤3cm).

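### SAP 7.6.1 gives each arm's Week 12 castration rate an asymptotic 95% CI with no formula named; if it is the Wald interval, it covers about 92% on average at the rates this trial expects

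*SAP*

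**What the plan says.** SAP 7.6.1 summarises the number and percentage castrated in each arm at Week 12 and adds that "its 95% asymptotic CI will be summarised for each treatment group at Week 12". It does not say which asymptotic formula is meant. It also gives no rule for a limit above 100% or for an arm in which every subject is castrated. SAP 7.1 asks for confidence limits of rates to two decimals.

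The same paragraph of SAP 7.6.1 does name the method for the between-arm difference: Miettinen and Nurminen, stratified, with an unstratified version in support. The analysis is run on the PP set and repeated on the FAS.

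The documents place the expected rates close to 100%. Protocol 1.3 reports from the earlier European study that "97% of subjects receiving triptorelin pamoate PR 3-month were castrated at Week 12, compared to 94% receiving the 1-month formulation". SAP 2.3 plans on a similar level: "Assuming the percentage of subjects castrated at Week 12 of triptorelin acetate PR 1-month treatment is no less than 92" per cent.

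SAP 7.6.3 adds that the primary and most secondary endpoints "will be analysed by subgroups of randomisation stratification factors", namely surgical history and baseline VAS. It gives no subgroup sizes and does not say whether the per-arm interval is repeated there.

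**The concern.** Applied to a single proportion, the word asymptotic is most often read as the Wald interval, the estimate plus or minus 1.96 estimated standard errors. Near 100% that interval behaves badly. It is symmetric where the sampling distribution is skewed, it can run past 100%, and it shrinks to a point when no failures are seen.

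The percentage castrated is itself the primary endpoint, and this is the only per-arm interval the SAP states for it. An interval labelled 95% that covers less, with a lower limit that tends to sit too high, makes each formulation's castration rate look better established than it is. An upper limit such as 100.27% in the primary table would also be an avoidable embarrassment.

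**Working it through.** **Inputs.** True rates of 92% (SAP 2.3), 94% and 97% (Protocol 1.3). Evaluable subjects: 133 per arm (SAP 2.3), up to the 150 per arm randomised. Wald is assumed for the unnamed formula. Subgroup arm sizes of 20, 30 and 50 are assumed, because the documents give none.

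**Step 1. Reproduce the plan's sample size.** With 92% in both arms, a margin of 10 points and one-sided 0.025:

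n = (1.960 + 1.036)² × 2 × 0.92 × 0.08 / 0.10² = 132.16, so 133 per arm.

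Power at 133 is 85.2%. Allowing for 10% dropout, 133 / 0.9 = 147.8, so 148 per arm or 296 in total, consistent with 300. The stated figure reproduces, and 133 to 150 is the right range for a full arm.

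**Step 2. Formulas**, with p̂ = x/n and z = 1.96.
- Wald: p̂ ± z √(p̂(1 − p̂)/n).
- Wilson: [p̂ + z²/(2n) ± z √(p̂(1 − p̂)/n + z²/(4n²))] / (1 + z²/n).
- Clopper-Pearson: exact limits from the beta distribution.
- Coverage at true rate p: the sum of the binomial(n, p) probabilities of every x whose interval contains p.

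**Step 3. One point by hand: n = 133, p = 0.97.** For x = 132, p̂ = 99.25% and the Wald lower limit is 97.8%, above 97%. For x = 133 the interval is 100% to 100%. Both miss. Their probability is 133 × 0.03 × 0.97¹³² + 0.97¹³³ = 7.2% + 1.7% = 8.9%. Misses on the other side (x of 123 or fewer) add 0.7%. Coverage is 100 − 8.9 − 0.7 = 90.4%.

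**Step 4. Exact coverage (%).**

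| n per arm | true rate | Wald | Wilson | Clopper-Pearson |
|---|---|---|---|---|
| 133 | 92% | 95.0 | 94.7 | 96.4 |
| 133 | 94% | 90.0 | 95.9 | 97.4 |
| 133 | 97% | 90.4 | 93.5 | 96.3 |
| 150 | 92% | 95.2 | 95.2 | 96.6 |
| 150 | 94% | 94.1 | 94.5 | 96.3 |
| 150 | 97% | 93.6 | 95.2 | 97.4 |

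Single points jump with n and p, so the average over a fine grid of true rates from 92% to 97% is the fairer summary:
- Wald: 92.1% at n = 133 (range 85.0 to 95.3) and 92.2% at n = 150 (range 85.4 to 95.2).
- Wilson: 95.3% at both sizes (range 93.1 to 97.1 at n = 133).
- Clopper-Pearson: 96.9% and 96.8%, never below 95%.

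**Step 5. Direction of the error.** On the same grid the Wald lower limit lies above the true rate in about 7% of samples at either size, against a nominal 2.5%. At n = 133 it does so in 4.0% of samples at a true rate of 92%, where two-sided coverage looks correct, and in 9.4% at 94%.

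**Step 6. Limits above 100%.** With k subjects not castrated, the Wald upper limit exceeds 100% when 0 < k < z² p̂. Since z² = 3.84, at these rates that means k = 1, 2 or 3: 130 to 132 of 133 (97.7% or more observed), or 147 to 149 of 150. At n = 133 the probability is 0.5%, 3.8% and 41.5% at true rates of 92%, 94% and 97%.

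**Step 7. Zero width.** This needs k = 0, with probability pⁿ. At n = 133 it is below 0.1% at 92% and 94%, and 1.7% at 97%. In subgroup arms of assumed size:

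| assumed n | zero width at 92% | zero width at 97% | Wald coverage at 97% |
|---|---|---|---|
| 20 | 19% | 54% | 46% |
| 30 | 8% | 40% | 60% |
| 50 | 2% | 22% | 78% |

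**Step 8. What a table would show (%).**

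| castrated | Wald | Wilson | Clopper-Pearson |
|---|---|---|---|
| 129/133 | 94.09 to 99.90 | 92.52 to 98.82 | 92.48 to 99.17 |
| 130/133 | 95.22 to 100.27 | 93.58 to 99.23 | 93.55 to 99.53 |
| 30/30 | 100 to 100 | 88.65 to 100 | 88.43 to 100 |

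**The case against.** The strongest reply is that nothing is decided on this interval. SAP 7.6.1 and Protocol 10.3 and 10.4.6.1 confirm non-inferiority only from the lower limit for the difference, and the protocol asks for no per-arm interval at all. That stands: the point concerns reporting, and a reader who inferred that the trial's conclusion is in doubt would be wrong.

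A second reply is that the SAP never says Wald. Wilson is also an asymptotic interval and has none of these three defects. That stands too. A reader might infer that the plan prescribes a faulty interval; what it actually does is leave the choice to whoever programs the table. Either way the remedy is to name the method.

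Third, a reader might infer that coverage is poor throughout, or that full-arm intervals will routinely pass 100%. The figures do not support this. Coverage is nominal at the 92% planning rate, and at n = 150 it is 94.1% and 93.6% at the two earlier-study rates. In a full arm, passing 100% needs an observed rate just above any that the documents quote. The shortfall is an average over the plausible range.

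Fourth, the subgroup figures rest on assumed sizes, and a per-arm interval in the subgroups is implied rather than stated. They show what could happen and are not predictions for this trial.

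**Conclusion.** The point holds as a reporting weakness in the primary table. The per-arm Week 12 interval is unspecified. On the usual Wald reading it covers about 92% on average over true rates of 92% to 97%, at 133 or 150 per arm, with a worst case near 85%. The error leans one way: the lower limit is too high in about 7% of samples instead of 2.5%. Limits above 100% are unlikely in a full arm at true rates of 92% to 94% and common at 97%. Zero-width intervals are a realistic risk only in smaller subgroups.

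This rests on two assumptions: that the unnamed formula is Wald, and, for the subgroups only, the sizes used. The non-inferiority decision is untouched.

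A reader might also extend the point to Weeks 4, 8 and 24. SAP 7.6.2 and 7.6.4 list only counts and percentages per arm there, with an interval for the difference, so no per-arm interval is planned that would need correcting.

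**What to change.** In SAP 7.6.1, name the per-arm interval: a 95% Wilson score CI for each arm's Week 12 castration rate, in the PP set and the FAS. Clopper-Pearson is an acceptable alternative if guaranteed coverage is preferred; it is slightly conservative, at about 97% on average. Add one sentence that the same method applies wherever else a per-arm castration interval is shown, including the subgroups in SAP 7.6.3. This need not add intervals at Weeks 4, 8 or 24.

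The cost is one phrase in the SAP and one option in the table program. Sample size, data collection, the margin and the decision rule stay as they are.
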